Appendix 3. Therapist assessment tool

Name	
Accreditation Body	
Profession	Counsellor/Psychotherapist/Psychologist *delete where appropriate
Date accredited	
Main therapeutic modality	
Other therapy training	
Years working with Simple PTSD	
Years working with Complex PTSD	
Other Professional qualifications e.g.	
Social Worker; Nurse etc	

Methodology used for therapist competency groupings

Therapists were asked to complete a self-assessment profile of therapist competence (Blackburn et al, 2001 (81)).

Additional demographics were collected of

- Professional Accreditation body
- Date of accreditation
- Main therapeutic modality(s)
- Other Therapeutic training
- Therapeutic experience of simple PTSD (years)
- Therapeutic experience of complex PTSD (years)
- Other Professional qualifications

No therapist was known to the Rater and data were sorted by level of competence self-rating resulting in 4 groupings. When the groups were reviewed and additional experience of working with complex PTSD and length of time since initial accreditation were factored in, 5 groups emerged.

Group 1 (level 1) consisted of newly accredited counsellors with limited experience of working with simple or complex PTSD, and a self rating of competent across the majority of skills.

Group 2 (level 1+) were counsellors who had been accredited for 5 years, including 5 years' experience of working with simple and complex PTSD. Self-rating spanned the competent and proficient skills for generic counselling skills and novice or advanced beginner for CBT and NLP specific competencies.

Group 3 (level 2) counsellors had minimum 8 years post accreditation experience and 9+ years' experience of working with simple and complex PTSD. Counsellors rated proficient in generic competencies and competent or proficient in CBT and NLP specific competencies.

Group 4 (level 2+) counsellors had minimum 11 years post accreditation experience, a post graduate qualification and 10+ years' experience of working with simple and complex PTSD. Counsellors rated proficient in generic competencies.

Group 5 (level 3) counsellors had minimum 10 years post accreditation experience, rated expert in generic and NLP/CBT competencies and had an additional professional registration to that of counselling or psychotherapy.

Self assessment

This self assessment table has been adapted from Blackburn et al (2001) (81) for the competency rating scale. The skill set is a generic therapeutic skill set identified by IAPT.nhs.uk.

Skill	Novice	Advanced	Competent	Proficient	Expert
		beginner			
Knowledge and understanding of					
mental health problems					
Knowledge of, and ability to operate					
within, professional and ethical					
guidelines					
Knowledge of a model of therapy,					
and the ability to understand and					
employ the model in practice					
Ability to engage the client					
Ability to foster and maintain a good					
therapeutic alliance, and to grasp					
the client's perspective and 'world					
View					
Ability to deal with emotional					
Content of session					
Ability to manage endings					
Ability to undertake generic					
identifying suitability for					
intervention)					
Ability to make use of supervision					
Pacing and leading and able to put					
client into a positive state by altering					
your own state					
Able to calibrate change in state of a					
client					
Elicitation of structures of present					
state					
Elicitation and assessment of					
associated vs dissociated trauma story					
Able to conduct a Symptoms of					
Distress Scale assessment in vivo					
Utilisation of anchoring techniques					
Utilisation of submodalities (finer					
distinctions of internal imagery) to					
effect change in clients					
Able to assist clients to dissociate and					
associate to and from states					
Able to identify trauma hot spots					

Appendix 4. Progression criteria to a full non-inferiority RCT

Project	Measure of Success	Nature and number of	Timescale
Outcome 1:	In 14 months we identify 180 eligible	180 study participants	Months 5-18
Known rate of	narticinants		WOII(II3 J-10
trial			
recruitment,	Consenting and randomised	60 study participants	Months 5-18
retention in	participants $n = 60$		
treatment and	Treatment drop out:	>36 study participants	Months 5-21
research and	RTM protocol Intervention drop out ≤		
completeness	30%		
of outcome	TF-CBT intervention drop out ≤ 50%		
data assessed	Research attrition: Research follow up	36 study participants	At end of project
against our	retention 36 participants at 20 weeks		
green traffic			
light			
Outcome 2:	Baseline data set is complete for 90%	54 study participants	Months 5-18
Exploratory	of participants	54 study participants	WOIIIIIS 5-18
analyses of the	12 week follow up data set is complete	42 study participants	Months 8-21
outcome data	for 70% of study participants		
to support a	20 week data set is complete for 50%	30 study participants	At end of project
nower	of participants		
calculation for			
a fully powered			
non-inferiority			
trial.			
Outcome 3:	A trial adverse and serious adverse	All 60 trial participants	Month 2
Known safety	event definition and safety protocol is		
risks and	developed which identifies all		
amenorations	refers according to Inspire and		
ОГКПИТНЕГАРУ	research project-specific statutory care		
	pathways: contains adverse events (e.g.		
	relapse, hospital admission, suicide		
	and attempted suicide) across the 20		
	week follow-up period and		
	documented clinical actions taken to		
	mitigate participant risk		
	All adverse and serious adverse events	All 60 trial participants	Month 5-23
	and ameliorations recorded and every		
	event discussed at the bi-weekly		
	research team meeting.		
	A log of every adverse, serious adverse	All 60 trial participants	At end of project
	event and clinical and research team		
1	actions in response		

Outcome 4:	A minimum of 5 Inspire therapists will	The beneficiaries of an	Month 4
Establishment	complete the 20 hour masterclass and	expanded professional	
of expanded	be assessed as proficient in delivering	mental health capacity	
mental health	protocoled TF-CBT	across Northern Ireland	
care capacity	-	would be extensive.	
across	A minimum of 5 different Inspire		Month 4
Northern	therapists will complete the 70 hr RTM	Hitherto, TF-CBT has only	
Ireland to	training and be assessed as proficient	been available to veteran	
enable both	in delivering the RTM protocol	members of the Armed	
interventions	Inspire therapists attend two – four	Forces aftercare service in	Month 21
to be delivered	weekly clinical supervision sessions	Belfast which for the	
within 20 miles		majority of veterans was	
of the		too far to travel weekly for	
veteran's		8-12 weeks.	
home.	≥50% of randomised participants to		At end of project
	the TF-CBT arm remain in treatment		
	when delivered closer to home		

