3.2 Research questions

- a. Can Inspire therapists deliver both interventions according to their respective protocols?
- b. Will statutory and charity sectors refer to an experimental NLP-based therapy and by which referral pathway?
- c. What is the rate of presentation of veterans with diagnosed PTSD, comorbidity and Complex PTSD to Inspire in Northern Ireland (NI)?
- d. What is the level of complete and missing data and on which outcomes?
- e. Are the progression criteria met, specified as recruitment of 60 participants in 14 months; in each arm ≥70% of participants complete treatment; retention of ≥36 participants at 20 week follow-up?
- f. How does the safety protocol (see appendix 1) detect and limit the consequences of adverse events and what are the clinical governance implications of this?
- g. What is the per-participant cost of delivering RTM (including managing any adverse or serious adverse events)?

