3.6 Sample Size

The proposed external pilot sample size takes into account published recommendations for pilot trials (42, 43) which propose a method for determining an external pilot RCT sample size in order to minimise the sample size for the main RCT. This sample size will support the calculation of confidence intervals around the proportion of eligible participants who agree to take part in the research, and the attrition rates from both the treatments and the research. Our proposed sample size is 60, 30 in each arm. Initially, we had a 1:1 randomisation ratio. However, with 50% of our target randomisation figures achieved due to therapist attrition in the TF-CBT delivery arm we sought statistical advice and decided to change the randomisation ratio to 2:1 in favour of the experimental RTM. This would allow us to continue to recruit at the level required to fulfil our recruitment targets specified by our funder.

Treatment seeking in the veteran population is low (44, 45) and response rates to PTSD research invitations are poorly reported (46, 47). For example, Ulmer et al (2011) (48) screened 91 veterans with PTSD to recruit 22 participants to their pilot RCT. In a review of 7 randomised trials comparing TF-CBT with Eye Movement Desensitisation and Reprocessing, research and treatment attrition ranged from 8 - 58% with a mean of 29% (49). Taking these data into account, we propose to screen 180 people for eligibility, randomise 60 participants and expect an attrition of 30% and 50% (or lower) from the intervention and comparison respectively resulting in \geq 36 participants with data at 20 weeks follow up. A screening sample of 180 would be sufficient to obtain a 95% confidence interval for a

proportion of $\pm 8\%$ or narrower, and a sample of 60 for a 95% confidence interval of $\pm 13\%$ or narrower, both with 99.9% probability calculated using SAS POWER (50)

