- On receipt the researcher will score the PCL-5. If the person scores ≥33, they will be given the opportunity to ask questions in person, electronically or over the phone. If they wish to proceed the researcher will undertake informed consent in person, electronically or over the phone. Consent will be recorded in writing by wet ink, electronically or audio recorded.
- 3. If the person declines to participate or if their PCL-5 score is <32 and therefore screened ineligible to take part, the researcher will inform them of this and ask permission to inform ACS so their caseworker can proceed with appropriate referrals. Alternatively, the person will be invited to inform their caseworker directly. All personal data on these people will be shredded/electronically deleted.

- 4. Each participant will then self-complete baseline data collection with researcher support as needed in person, electronically or over the phone.
- 5. An appointment will be made for them with the Inspire Clinical Psychologist within two weeks to have a confirmatory PTSD diagnostic interview.
- 6. Once eligibility is confirmed they will be computer randomised to a therapy group and commence therapy within two weeks.
- 7. Those not eligible will be referred back to ACS by Inspire.

Pathway B) For all other recruitment routes

- 1. All public engagement, traditional and online social media announcements relating to the PETT study will contain the information video link and email address [contact].
- 2. Once a potential participant contacts the team they will be contacted by a named researcher who will offer the PETT study invitation letter, a copy of the PCL-5, a personal data processing consent form and the participant information sheet. They will be given the opportunity to ask questions and can complete the PCL-5 in person, over the phone or electronically. They will be made aware that if they experience distress in relation to completing the PCL 5, they can contact the researcher who can signpost them to support. Support organisations are also listed on the study invitation letter and in study emails.

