- 3. If the person declines to participate or if their PCL-5 score is ≤ 32 they will be signposted to organisations, including Inspire and their GP, who they may wish to contact about further mental health assessment and treatment. In addition, if we know that they are currently being seen by a veteran charity organisation the person will be invited to inform the organisation or their caseworker directly. All personal data on these people will be shredded/electronically deleted.
- If the person's PCL-5 score is ≥ 33 the researcher will proceed to undertake informed consent in person, electronically or over the phone. Consent will be recorded in writing by wet ink, electronically or audio recorded.
- 5. The participant will then self-complete baseline data collection with the researcher support if needed in person, electronically or over the phone.
- 6. Following informed consent and baseline data collection an appointment will be made for them with the Inspire Clinical Psychologist within two weeks to have a confirmatory PTSD diagnostic interview.
- 7. Once eligibility is confirmed they will be computer randomised to a therapy group and commence therapy within two weeks.
- 8. For those ineligible the Clinical Psychologist will discuss, and signpost to other therapeutic options. If the participant is been seen by a veteran charity organisation they will be invited to inform the organisation or their charity caseworker directly.

Inspire receive on average 10-15 referrals per month from ACS meeting our eligibility criteria. Screening, on average, 13 veterans every month for 14 months equals 182 potentially eligible participants. We realistically estimate that 4-5 of these 13 potentially eligible veterans will consent to join the study, therefore we will be able to recruit and randomise 60 participants in 15 months.

We will offer a £15 high street voucher as a *thank you* to all participants who complete each of the 6, 12, 20 and 52 week questionnaire booklets. The maximum voucher value will be £60 per participant.

The veteran community is well-networked, and messaging about the trial aims and procedures must be well thought out and transparent to limit misinformation affecting recruitment and consent to randomisation (see appendix 2 for Stakeholder engagement protocol).

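### The progression criterion of 180 eligible people in 14 months does not match the plan to screen 180, and the ±8% precision and the recruitment period need the same alignment

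*Protocol*

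**What the plan says.** - **Protocol, Appendix 4, Outcome 1:** "In 14 months we identify 180 eligible" participants (months 5 to 18). A separate row asks for 60 consenting and randomised participants over the same months.
- **Protocol 3.6:** "we propose to screen 180 people for eligibility, randomise 60 participants". The sample is meant to support "confidence intervals around the proportion of eligible participants who agree to take part in the research". On precision: "A screening sample of 180 would be sufficient to obtain a 95% confidence interval for a" proportion of ±8% or narrower.
- **Protocol 3.7:** about 13 veterans screened per month for 14 months give 182 potentially eligible people, of whom 4 to 5 in every 13 are expected to consent; "therefore we will be able to recruit and randomise 60 participants in 15 months".
- **Protocol 3.7, both pathways:** the order is PCL-5 screen, consent, baseline data, diagnostic interview, and then "Once eligibility is confirmed they will be computer randomised to a therapy group and commence therapy within two weeks".
- **Protocol 3.5 and Appendix 1, 6.1:** the clinical psychologist determines eligibility at the clinical assessment.
- **Protocol 3.2(e):** the progression criteria include "recruitment of 60 participants in 14 months".

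**The concern.** One number, 180, stands for three groups: people screened (3.6), people potentially eligible (3.7, as 182) and people eligible (Appendix 4). These are different stages of the participant flow, and Appendix 4 does not say which one its threshold counts. The same ambiguity affects precision, because section 3.6 sizes an interval on the screened but names a proportion among the eligible. The recruitment period is 14 months in two places and 15 in another.

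The Appendix 4 criteria decide whether a full trial is judged deliverable. A threshold whose meaning is open can be read as failed or passed once the counts are known. The consent rate that the pilot hands to the full trial would also have an unstated denominator.

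**Working it through.** **1. The plan's own figures.** Flow: 13 × 14 = 182, as stated in 3.7. Precision for 180 screened at the worst case p = 0.5: 1.96 × √(0.25/180) = 7.3% (Wald); the exact (Clopper-Pearson) maximum is 7.5%. Both are within ±8%, so the figure is right for the denominator that 3.6 gives it.

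**2. What 180 would mean at each stage over 14 months.**

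| Meaning of eligible in Appendix 4 | Projection from 3.7 | Is 180 reached? |
|---|---|---|
| Referrals described as meeting the criteria | 10–15 × 14 = 140–210 | Within range; needs 180/14 = 12.9 per month |
| People screened | 13 × 14 = 182 | Yes, just |
| PCL-5 of 33 or more among those screened | at most 182 | Only if 180/182 = 99% pass |
| Confirmed by the psychologist after consent | 4–5 × 14 = 56–70 at most | No; about a third of 180 |

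On the last meaning the criterion also conflicts with the next row of Appendix 4. Those confirmed eligible go on to randomisation, so 180 confirmed would imply about 180 randomised rather than 60.

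**3. Screening needed to find 180 eligible, and precision if 180 are screened.** The protocol gives no eligible fraction e, so it is an assumption, shown over a range. Number to screen = 180/e; half-width = 1.96 × √(0.25/(180e)).

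| e | Screen to find 180 eligible | Eligible among 180 screened | Half-width at p = 0.5 |
|---|---|---|---|
| 0.9 | 200 | 162 | 7.7% |
| 0.8 | 225 | 144 | 8.2% |
| 0.7 | 258 | 126 | 8.7% |
| 0.6 | 300 | 108 | 9.4% |
| 0.5 | 360 | 90 | 10.3% |

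Denominator needed for ±8% at p = 0.5: 1.96² × 0.25/0.08² = 150.06, so 151, and 151/180 = 84%. With the exact interval it is 160 (89%). At p = 60/180 = 1/3 it is 1.96² × 0.2222/0.0064 = 133.4, so 134 (74%).

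**4. Accrual.** The 14-month target needs 60/14 = 4.3 randomised per month. Consents in 14 months are 4 × 14 = 56 to 5 × 14 = 70, with a midpoint of 4.5 × 14 = 63. At 4 per month, 60 takes 60/4 = 15 months. Section 3.7 goes from people consenting to people randomised with no loss at the diagnostic interview, although both pathways provide for people found ineligible there. The largest loss that still leaves 60 randomised in 14 months is:

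- 70 consents: 1 − 60/70 = 14%
- 63 consents: 1 − 60/63 = 5%
- 56 consents: none, because 56 < 60

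The protocol gives no diagnostic loss. Assumed losses of 0%, 10% and 20% turn 56–70 consents into about 56–70, 50–63 and 45–56 randomised.

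**The case against.** A reader might infer that the criterion is unattainable however recruitment goes. The documents do not support that. They also use eligible for people before consent: section 3.7 describes 10 to 15 monthly referrals from one source as meeting the eligibility criteria, section 3.12.2 counts eligible people who are referred or self-refer separately from those who consent, and a low PCL-5 is called screened ineligible. The separate row for 60 consenting and randomised suggests that the 180 is a pre-consent pool. The 180 and 182 are projections and not caps, and other referral routes and UK-wide recruitment add to them.

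A reader might also infer that the ±8% is wrong, or that consent among the eligible cannot be estimated. Neither follows. The ±8% reproduces and is labelled as a screening-sample figure. PCL-5 status is known before consent, so consent among screen-positives can be estimated; only consent among the diagnostically confirmed cannot, because decliners never reach the interview.

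Finally, section 3.2(e) lists the progression criteria without any 180, and the midpoint accrual of 63 exceeds 60.

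All of this stands, and it limits the point. It does not remove the mismatch. The referral reading is itself weak: inclusion criterion 3 requires a CAPS-5 diagnosis, section 3.5 says the charity does not routinely conduct such interviews, and section 3.7 then calls the same people only potentially eligible. Appendix 4 still lists the 180 as a measure of success.

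**Conclusion.** The point holds as an inconsistency in a decision threshold. Appendix 4 requires 180 eligible where the plan screens 180. Whether the threshold can be met depends on an undefined word: the projection is 140–210 for referrals and 182 for people screened, PCL-5 positives would need a 99% pass rate, and confirmed eligibility yields at most 56–70.

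The ±8% is sound for those screened. It transfers to the named proportion only if about 84% of the 180 are eligible (p = 0.5, Wald), or 74% at p = 1/3. The protocol gives no eligible fraction, so neither failure nor success of that transfer can be asserted.

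The 14- and 15-month periods contradict each other. The low end of the planning range, 56 consents, misses 60 in 14 months even with no loss at the interview. The correction is worth making before progression is judged, but it does not put the design or the sample size in question.

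**What to change.** - **Appendix 4, Outcome 1:** restate the criterion as 180 people screened (PCL-5 returned) in months 5 to 18.
- **Section 3.6:** tie the ±8% to the 180 screened. In place of "the proportion of eligible participants who agree to take part in the research", report consent among PCL-5 screen-positives and randomisation among those consenting, each with its own denominator and interval. With 56 to 70 consenting, the second has a half-width of up to 13.1% to 11.7% (Wald, p = 0.5).
- **Sections 3.2(e) and 3.7 and Appendix 4:** use one recruitment period and restate the monthly randomisation rate it needs (4.3 for 14 months, 4.0 for 15), with the assumed conversion from consent to randomisation.
- **Screening record:** keep an anonymous count at each stage, since section 3.7 deletes the personal data of decliners and of those screened out.

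The cost is wording and a tally; no procedure or sample size changes. The downside is that the accrual requirement and the precision of the consent rate are stated slightly less favourably.

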Appendix 5: Data source and input responsibilities for trial database

MACRO Database form	Data source	Person entering data into database	Baseline	6 weeks	12 weeks	20 weeks	52 weeks	Comments
			TRIA	DATABASE (BL	INDED)			
1.Registration	Consent form	Person taking consent or FTR	x					
2.Eligibility	CP records	CP or FTR	Х					
3. Socio- demographic	Baseline Outcome Data Booklet	BR	x					
4.PTSD history	CP records	CP or FTR	Х					
5.Status form	Follow up contacts	BR		X	X	X	x	
6.PCL-5	- Inspire assessment records or Baseline Outcome Data Booklet - Follow-up Outcome Data Booklet	CL/CP/UBR/BR	X CL/CP	X Th/UBR/BR	X Th/UBR/BR	X BR	X BR	
7.WSAS	- Baseline Outcome Data Booklet - Follow-up Outcome Data Booklet	BR	X	X	X	X	X	

The PETT study has been funded by the Forces in Mind Trust (FiMT), a £35 million funding scheme run by the FiMT using an endowment awarded by The National Lottery Community Fund.

8.EQ-5D-5L	- Baseline Outcome Data Booklet - Follow-up Outcome Data Booklet	BR	X	X	X	X	X	
9.Adapted Folated	- Baseline Outcome Data Booklet - Follow-up Outcome Data Booklet	BR	X	X	X	X	X	
10.PHQ9	- Inspire assessment records or Baseline Outcome Data Booklet - Follow-up Outcome Data Booklet	CL/CP/UBR/BR	X	X	X	X	X	
11.GAD7	- Inspire assessment records or Baseline Outcome Data Booklet - Follow-up Outcome Data Booklet	CL/CP/UBR/BR	X	X	X	X	X	
12.QRP	- Baseline Outcome Data Booklet	BR	X	X	X	X	X	

	- Follow-up Outcome Data Booklet							
13.Randomisation	Eligibility (2)	BR	Х					
14. Ongoing MH meds	Follow-up Outcome Data Booklet	BR		X	X	X	X	NB: These questions risk unblinding the BR. Therefore BR does not look at or enter Questionnaire 8 data. This data is passed to UBR who will enter the data in the Therapies database.
15.Alternative therapies log	Follow-up Outcome Data Booklet &/or Inspire records	BR		X	X	X	X	NB: These questions risk unblinding the BR. Therefore BR does not look at or enter Questionnaire 8 data. This data is passed to UBR who will enter the data in the Therapies database.
16.Adverse Events log	Therapist database &/or ICP &/or GP &/or participant See comments	BR/UBR	Ongoing t	hroughout trial				During therapy from Inspire &/or ICP &/or from participant in Questionnaire 8 in Follow-up Outcome Data Booklet . During follow up from Participant in Questionnaire 8 in Follow-up Outcome Data

								Booklet and/or from GP or ICP.	
17. Withdrawal	Follow up contacts	BR		x	x	Х	x		
18. PI database signoff	Completed database	PI & Trial manager ([name])				X	X		
